8.5.4 Adverse Event Reporting to Ultragenyx

8.5.4.1 General

All AEs (i.e. any new or worsening in severity or frequency of a preexisting condition) with onset after the subject signs consent for study participation must be promptly documented on the AE eCRF via the EDC system. The Principal Investigator is responsible for evaluating all AEs, obtaining supporting documents, and ensuring documentation of the event is adequate. Details of the AE must include severity, relationship to study drug, duration, and outcome.

All AEs will be collected from the time the subject signs the informed consent through 30 days following the last dose of study drug, or, if applicable, until the date the subject signs the informed consent for the open-label extension study, UX001-CL302, whichever occurs sooner. In addition for those subjects choosing not to enroll in UX001-CL302, the Investigator should report any AE that occurs more than 30 days following the last dose of study drug that is believed to have a reasonable possibility of being associated with study drug.

AEs ongoing after the defined follow-up period stated in the paragraph above should have a comment in the source document by the Investigator that the event has recovered, recovered with sequelae, or stabilized.

8.5.4.2 Serious Adverse Events, Serious Adverse Drug Reactions, and Requirements for Immediate Reporting

Any SAE that occurs at any time during the study, including a clinically significantly abnormal laboratory test result that is considered serious, must be reported within 24 hours of knowledge of the event to Ultragenyx or its designee. These requirements apply equally to all subjects, regardless of the study phase or the at-risk subject's treatment assignment or dosage. The reporting requirement for SAEs is from the time of signing of the ICF through 30 days following the last study drug administration.

SAEs will be reported by completing and submitting SAE report forms to Ultragenyx or its designee. Initial SAE reports must be followed by detailed descriptions. These should include copies of hospital case records and other documents when requested. Follow-up SAE information must be submitted in a timely manner as additional information becomes available. All SAEs regardless of relationship to study drug must be followed to resolution or stabilization if improvement is not expected.

A death occurring during the study, during the per-protocol follow-up period, or within 30 days after stopping treatment with the study drug must be reported to Ultragenyx or its designee within 24 hours of knowledge of the death whether or not it is considered treatment-related.

The investigator also must notify the IRB/EC of the occurrence of the SAE, in writing, as soon as is practicable and in accordance with IRB/EC requirements and local law. A copy of this notification must be provided to Ultragenyx or its designee.

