5.3 Summary of Overall Risks and Potential Benefits

Since SA is a normal body compound with native pathways for degradative metabolism and rapid renal clearance, there is no evidence or expectation of a significant safety issue with SA replacement therapy at this time. Data from nonclinical and clinical studies to date suggest SA-ER administered alone or with SA-IR does not pose any significant safety risks that can be identified at this time. Toxicology or adverse pharmacology findings were not observed in SA-treated animals; at very high doses, osmotic diarrhea may be observed in treated dogs. Interim safety results following a 24-week Treatment Period in a completed Phase 2 study (UX001-CL201), suggested an increase in diarrhea and GI symptoms relative to placebo. No correlation was observed between the GI events and free SA serum levels suggesting the frequency of GI events does not appear to be dose dependent.

In patients with GNE Myopathy, replacement of the substrate SA has the potential to restore normal sialylation of muscle glycoproteins and glycolipids, which could improve the function of muscle and limit the loss of muscle strength. It is not clear how much the effects of GNE Myopathy are reversible or if and how fast reversal of muscle disease might occur. The data in the HIBM mouse model suggest that over a one year period, substantial beneficial effects on the pathology of the disease are possible. However, it is not clear

whether advanced disease can improve, as opposed to preventing progression of existing disease. If the therapy has an effect comparable to that observed by Sparks and colleagues using intravenous immune globulin (IVIG) as a source of SA ([Sparks et al. 2007](#)), then the benefit to GNE Myopathy patients in improving muscle strength and function might be substantial. In clinical studies conducted to date, the highest dose (6g/day SA-ER) provided a sustained exposure, a clinical efficacy signal, and acceptable safety profile. Overall the risk-benefit ratio appears to be favorable based on the excellent safety record to date, and the potential benefit observed in nonclinical and clinical studies.

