7.6.2 Safety Measures

The safety measures in this study are:

- Incidence and frequency of AEs and SAEs
- Clinically significant changes from baseline in vital signs, physical and neurological examination findings and laboratory evaluations
- Interval history, including reported symptoms of increasing muscle weakness or pain, and incidence of falls

The analyses of safety will include all subjects who receive any study drug at any time during the study and provide any post-treatment safety information. Safety data will be periodically reviewed by the DMC.

For the safety analysis, the incidence and frequency of AEs and SAEs will be evaluated. All AEs will be coded using the Medical Dictionary for Regulatory Activities (MedDRA). The incidence and frequency of AEs will be summarized by System Organ Class (SOC), Preferred Term (PT), relationship to study drug, and severity for each treatment group. A by-subject listing will be provided for those subjects who experience a SAE, including death, or experience an AE associated with early withdrawal from the study or study drug.

Clinical laboratory data will be summarized by the type of laboratory test. The frequency and percentage of subjects who experience abnormal clinical laboratory results (i.e., outside of reference ranges) and/or clinically significant abnormalities after study drug administration will be presented for each clinical laboratory measurement. For each clinical laboratory measurement, descriptive statistics will be provided for Baseline and all subsequent post-treatment scheduled visits. Changes from Baseline to the post-treatment visits will also be provided. Descriptive statistics of vital signs, imaging assessments, and concomitant medications will also be provided in a similar manner.

The SAP will provide additional details on the planned statistical analysis.

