6.5.3 Derived Safety, Dosing, and Medication Variables

Non Treatment Emergent Adverse Events (AEs) include all adverse events that stopped the day prior to the start of study medication, started prior to the start of study medication but did not increase in severity or relationship during treatment, or started more than 30 days after the final study medication dosing date. In this study there is no expectation on non-treatment emergent adverse events in any subjects who roll-over from UX0010-CL201. Subjects in the treatment naïve population may have non-treatment emergent adverse events recorded if an event occurs between screening (informed consent) and the first dose of planned study medication (12g.day SA-ER/SA-IR).

Treatment Emergent Adverse Events (TEAE) include all adverse events that start on or after the first dose of study medication, or adverse events that are present prior to the first dose of study medication, but their severity or relationship increases after the first dose of study medication up to and including 30 days after the final study medication dosing date.

Dosing: Number of doses administered will be calculated for each subject by summing the number of doses administered over all visits.

Medications:

Prior medications include all medications that are taken prior to the first dose of study medication date.

Concomitant medications include all medications that are taken on or after the date of first dose of study medication.

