6.10.1 Adverse Events

Adverse Events will be assessed at all visits and throughout the course of the study. The number and percent of subjects with any treatment-emergent adverse events (TEAEs) will be displayed by system organ class and preferred term for each treatment group (6g/day SA-ER, 12g/day SA-ER/SA-IR). Within each preferred term, subjects will be counted only once if they had more than one event reported during the treatment period. The same summary will be performed for all serious TEAEs and all TEAEs causing discontinuation of study drug.

The number and percent of subject TEAEs will also be summarized by greatest reported severity grade (Grades 1-5) for each event preferred term by treatment group. Wherever possible, the severity of all AEs observed will be graded using the NCI CTCAE (V4.0) as follows in [Table 9](#):

Table 9 NCI-CTCAE Common AE Grading Criteria

Grade	Description
1	Mild; asymptomatic or mild symptoms; clinical or diagnostic observations only; intervention not indicated.
2	Moderate; minimal, local or noninvasive intervention indicated; limiting age-appropriate instrumental ADL*.
3	Severe or medically significant but not immediately life-threatening; hospitalization or prolongation of hospitalization indicated; disabling; limiting self-care ADL**.
4	Life-threatening consequences; urgent intervention indicated.
5	Death related to AE.
Source: Common Terminology Criteria for Adverse Events (CTCAE), Version 4.0, Published May 28, 2009 (v4.03, June 24, 2010); USHHS/NIH/NCI * ADL=Activities for Daily Living: Instrumental ADL refer to preparing meals, shopping for groceries or clothes, using the telephone, managing money, etc. ** Self-care ADL refer to bathing, dressing and undressing, feeding self, using the toilet, taking medications, and not bedridden.	

The majority of AEs and TEAEs can be graded using the NCI-CTCAE system. Wherever possible, the severity of all AEs will be graded using the NCI CTCAE. The majority of AEs can be graded using this system. If an AE cannot be graded using the CTCAE criteria, it should be graded as mild, moderate, severe, life-threatening, or death using the definitions in Table 10.

Table 10 Mapped AE Grading Criteria

Grade	Description
Mild (Grade 1)	Awareness of signs or symptoms, but easily tolerated and of a minor irritant type, causing no loss of time from normal activities. Symptoms do not require therapy or a medical evaluation; signs and symptoms are transient.

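### The protocol makes AE frequency a safety measure alongside incidence, but the SAP's specified AE summaries count each subject once, so more frequent recurrence on 12 g/day would not show

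*Protocol*

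**What the plan says.** Protocol 7.6.2 lists "Incidence and frequency of AEs and SAEs" among the safety measures, says that "the incidence and frequency of AEs and SAEs will be evaluated", and sets out the breakdown: "The incidence and frequency of AEs will be summarized by System Organ Class (SOC), Preferred Term (PT), relationship to study drug", with severity, for each treatment group. Protocol 8.5.4.1 describes an AE as "any new or worsening in severity or frequency of a preexisting condition".

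SAP 6.10.1 tabulates TEAEs as the number and percent of subjects in a 6 g/day and a 12 g/day group. Within a preferred term, "subjects will be counted only once if they had more than one event reported during the treatment period". The severity summaries likewise count a subject once at each level, and severity and relationship are shown at the greatest value reported. In the table list (SAP 8.1), Tables 9-14 cover TEAEs, and none of their titles names an event count or rate. The second version of Table 10 is sorted by descending frequency of preferred term, which sets an order but does not specify an event count. SAP 6.10.5 counts falls by number.

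SAP 6.5.3 treats as not treatment-emergent an event that "started prior to the start of study medication but did not increase in severity or relationship during treatment". Frequency is not among the triggers.

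**The concern.** The AE signal that the protocol itself reports is of a kind that recurs: in Protocol 5.3 the 24-week results of the feeder study "suggested an increase in diarrhea and GI symptoms relative to placebo". The same section adds that GI events showed no correlation with free SA serum levels and infers that their frequency does not appear to depend on dose. That inference comes from a study of 3 g and 6 g/day. Part II gives 12 g/day, its safety is a stated objective (Protocol 6), and Protocol 7.2 says it is the first use of the combined product in these patients.

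The 6 g and 12 g TEAE columns are where a reader would look to check the inference. A once-per-subject count shows whether more subjects are affected. It does not show whether subjects already affected have the event more often. The protocol promises both.

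**Working it through.** The documents give no AE rate, power or alpha for this point, and safety is descriptive (SAP 6.10), so there is no plan figure to reproduce. The check compares what a subject count and an event count would show. Subject numbers and period lengths come from the documents. **All episode rates are assumptions.**

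**1. Recurrence in subjects already affected.** Inputs: 46 rollover subjects (Protocol 7.6.4); assume k of them have one episode each on 6 g/day and r episodes each on 12 g/day. Subject incidence is k/46 in both columns whatever r is. Events are k on 6 g and k × r on 12 g.

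| k | Incidence, 6 g and 12 g | Events on 6 g | Events on 12 g, r = 2 / 3 / 5 |
|---|---|---|---|
| 5 | 5/46 = 10.9% in both | 5 | 10 / 15 / 25 |
| 10 | 10/46 = 21.7% in both | 10 | 20 / 30 / 50 |
| 20 | 20/46 = 43.5% in both | 20 | 40 / 60 / 100 |

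The change in the specified table is 0 percentage points in every row.

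**2. Episodes falling at random over all subjects.** With a Poisson mean of m episodes per subject, incidence = 1 − exp(−m). Double the event rate, a true ratio of 2:

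| m → 2m | Incidence | Incidence ratio |
|---|---|---|
| 0.25 → 0.5 | 22.1% → 39.3% | 1.78 |
| 1 → 2 | 63.2% → 86.5% | 1.37 |
| 2 → 4 | 86.5% → 98.2% | 1.14 |
| 4 → 8 | 98.2% → 100.0% | 1.02 |

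The subject count follows the change fairly well for a rare event and hardly at all for a common, recurring one.

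**3. Why a raw event count is not enough.** Part I lasts about 12 weeks, which the protocol synopsis equates with 3 months; the main Part II analysis is at 6 months (SAP 6.3). If all 46 rollovers complete both, subject-time is 46 × 3/12 = 11.5 years on 6 g/day and 46 × 6/12 = 23 years on 12 g/day. Take k = 10:

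- 6 g/day: 10/11.5 = 0.87 events per subject-year.
- 12 g/day, 20 events: 20/23 = 0.87, ratio 1.0.
- 12 g/day, 30 events: 30/23 = 1.30, ratio 1.5.
- 12 g/day, 50 events: 50/23 = 2.17, ratio 2.5.

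Here a doubling of raw events from 10 to 20 is entirely the longer period. For a subject who stayed on 12 g/day for the full 36 months the time ratio would be 36/3 = 12. Actual time differs by subject: the note to SAP Figure 1 says that time in Part I varied and that some rollovers went straight to Part II, and Part III returns many to 6 g/day. The denominator therefore has to be each subject's time on each dose.

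**The case against.** **Frequency may simply mean the number of subjects.** Protocol 7.6.2 does not define it, and its laboratory paragraph uses the word for subjects with abnormal results. On that reading the SAP complies. But incidence and frequency would then be one measure named twice, and 8.5.4.1 uses frequency for recurrence. Recurrence is the better reading, though not the only possible one.

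**Nothing is lost.** This stands in part. SAP 6.10.1 lists all TEAEs and non-emergent AEs by subject, and falls are counted. The TEAE overall summary (Table 9) has unspecified content and the table shells are in a separate document, so it cannot be said that an event total appears in no planned table. The point is limited to what the SAP specifies.

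**It may be a version gap.** The SAP cites the protocol through Amendment 1; later amendments revised Sections 7.6 and 8.5.4. The statement of consistency in SAP 6.5.1 should therefore not be called wrong when written. The current texts still differ.

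**Stronger readings that a reader might infer:**

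- *Frequency-only worsening is excluded by rule in rollover subjects.* Not supported. Protocol 8.5.4.1 makes such a worsening an AE to be documented. Recorded with an onset on or after first dose, it meets the first limb of the TEAE definition. Only an increase kept on a record with a pre-dose start would be missed, and SAP 6.5.3 expects no non-emergent events in rollovers. Nor can a number of affected subjects be estimated, because the documents give no rates.
- *The summaries are biased in favour of 12 g/day.* Not established. Once-per-subject counting hides recurrence, but a longer period on 12 g/day raises the percent of subjects affected.
- *Adding frequency to the TEAE wording would be enough.* It would not. Protocol 8.5.4.1 says "Details of the AE must include severity, relationship to study drug, duration, and outcome", and SAP Table 5 lists no frequency variable, so a change on a continuing record could not be detected.

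**Conclusion.** The point holds for the AE summaries that the SAP specifies. They deliver incidence but not frequency, and the 6 g versus 12 g comparison does not respond to recurrence in subjects already counted. With assumed rates, a two- to five-fold rise in episodes among the same subjects changes the table by nothing, and a doubling of the rate over all subjects appears as a ratio between 1.78 and 1.02, depending on how common the event is. The true size in this trial cannot be derived from the documents.

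The conclusion rests on reading frequency as recurrence and on recurrences being entered as separate AE records; episodes merged into one record would be hidden from an event count too. The mismatch in the TEAE definition is a minor matter of harmonisation.

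**What to change.** 1. In SAP 6.10.1 and Tables 9-14, put the number of events beside the number and percent of subjects, and add events per subject-time on each dose, with the subject-time shown. Do not present raw counts alone, because the periods differ in length.
2. In SAP 6.5.3, for agreement with Protocol 8.5.4.1, state that a worsening in frequency is recorded as a new AE with its own onset date and is assigned to the dose being taken at that onset. The SAP does not now say which dose column takes an event that begins in Part I and becomes more frequent in Part II.

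Cost: one or two extra columns in tables already planned. The event counts use AE records already collected, and subject-time follows from dosing dates. The recording convention needs an instruction to sites and cannot recover increases already kept on a single record. The AE figures may look less favourable.

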8.5.4.3 Urgent Safety Reporting

The regulations governing clinical studies state that the sponsor and investigator are required to take appropriate urgent safety measures to protect subjects against any immediate hazards that may affect the safety of subjects, and that the appropriate regulatory bodies should be notified according to their respective regulations. According to the European Union (EU) Clinical Trial Directive 2001/20/EC, "...in the light of the circumstances, notably the occurrence of any new event relating to the conduct of the trial or the development of the investigational medicinal product where that new event is likely to affect the safety of the subjects, the sponsor and the investigator shall take appropriate urgent safety measures to protect the subjects against any immediate hazard. The sponsor shall forthwith inform the competent authorities of those new events and the measures taken and shall ensure that the Ethics Committee (EC) is notified at the same time." The reporting period for urgent safety issues is the period from the signing of the ICF through 30 days following the last dose of study drug. Investigators are required to report any urgent safety measures to Ultragenyx within 24 hours.

8.5.4.4 Adverse Drug Reaction Reporting

Ultragenyx or its designee will submit suspected unexpected serious adverse reactions (SUSAR) to appropriate Regulatory Authorities (including Competent Authorities in all Member States concerned), Ethics Committees, and Investigators as per local laws and regulations. Fatal and life-threatening SUSARs will be submitted no later than 7-calendar days of first knowledge of the event and follow-up information submitted within an additional eight (8) days. All other SUSARs will be submitted within 15-calendar days of first knowledge of the event.

Principal Investigators are required to report any urgent safety matters to Ultragenyx or its designee within 24 hours. Ultragenyx or its designee will inform the Regulatory Authorities, Ethics Committees, and Investigators of any events (e.g. change to the safety profile of UX001, major safety findings) that may occur during the clinical trial that do not fall within the definition of a SUSAR but may affect the safety of subjects participating in the clinical trials, as required, in accordance with applicable laws and regulations. The reporting period for urgent safety issues is the period from the signing of the ICF through 30 days following the last dose of study drug.

The investigator will notify the IRBs/Research Ethics Boards (REB)/ECs of SAEs and urgent safety matters, in accordance with IRB/REB/EC requirements and local laws and regulations. A copy of this notification must be provided to Ultragenyx or its designee.

Non-SUSARs will be maintained in the Ultragenyx safety database and provided in annual and/or periodic reports as per local laws and regulations. Ultragenyx or its designee will prepare and submit annual safety reports and/or other aggregate periodic summary reports to Regulatory Authorities and Ethics Committees, as per local laws and regulations.

8.5.4.5 Pregnancy in Subject or Partner

Pregnancies in subjects or partners must be reported within 24 hours of knowledge of the event to Ultragenyx or its designee. The reporting period for pregnancies is the period from the signing of the ICF through 30 days following the last dose of study drug.

Reported pregnancy of a subject or a subject's partner, while participating in the study, will be monitored for the full duration and/or followed until the outcome of the pregnancy is known. In the event of a pregnancy in the partner of a subject, the Investigator should make every effort to obtain the female partner's consent for release of protected health information. Pregnancy-associated SAEs will be processed and submitted, as necessary, as per the SUSAR reporting process (Section 8.5.4.4).

8.6 Financing and Insurance

Financing and insurance for this clinical trial will be addressed in clinical trial agreements with the study site.

8.7 Publication Policy

Any publication or presentation by the investigator and/or the Institution based on data or results resulting from the Ultragenyx study shall only be done in strict accordance with the Publication section in the Clinical Trial Agreement executed between Ultragenyx and the Institution and/or the investigator.

DMC	Data Monitoring Committee
DMRV	distal myopathy with rimmed vacuoles
EC	Ethics Committee
ELISA	enzyme-linked immunosorbent assay
EMG	electromyography
EU	European Union
EudraCT	European Union Drug Regulating Authorities Clinical Trials
FDA	Food and Drug Administration
GCP	Good Clinical Practice
GMP	Good Manufacturing Practice
GNE	glucosamine (UDP-N-acetyl)-2-epimerase
GNE-DMP	GNE Myopathy Disease Monitoring Program
GNE/MNK	glucosamine (UDP-N-acetyl)-2-epimerase/N-acetylmannosamine kinase
hERG	human ether-à-go-go-related gene
HHD	hand-held dynamometry
HIBM	hereditary inclusion body myopathy
HIBM-FAS	HIBM Functional Activities Scale
HIPAA	Health Insurance Portability and Accountability Act
IB	Investigator's Brochure

Abbreviation/Term	Definition
ICF	informed consent form
ICH	International Conference on Harmonisation of Technical Requirements for Registration of Pharmaceuticals for Human Use
IND	Investigational New Drug (application)
IRB	Institutional Review Board
ITT	Intent-To-Treat Population
IVIG	intravenous immune globulin
LDH	lactate dehydrogenase
ManNAc	N-acetyl-D-mannosamine
MCH	mean corpuscular hemoglobin
MCHC	mean corpuscular hemoglobin concentration
MCV	mean corpuscular volume
MedDRA	Medical Dictionary for Regulatory Activities
MMP9	matrix metalloproteinase 9
MRC	Medical Research Council
MUAP	polyphasic muscle unit action potential
MVIC	maximum voluntary isometric contraction
NANA	N-acetylneuraminic acid
NCAM	neural cell adhesion molecule
NCI CTCAE	National Cancer Institute Common Terminology Criteria for Adverse Events
NOAEL	no observed adverse effect level
PD	pharmacodynamic
PK	pharmacokinetic(s)
PT	Preferred Term
qHS	at the time of sleep (i.e., at bedtime)
QID	four times per day
QD	one time per day
RBC	red blood cell
SA	sialic acid
SAE	serious adverse event
SA-ER	Sialic Acid-Extended Release
SA-IR	Sialic Acid Immediate Release
SAP	Statistical Analysis Plan

Abbreviation/Term	Definition
SGOT	serum glutamic oxaloacetic transaminase
SGPT	serum glutamic pyruvic transaminase
SOC	System Organ Class
TID	three times per day
TNP	Treatment Niave Popultion
US	United States
WBC	white blood cell

